We will recruit older Veterans with dysvascular LLA (1-5 years after LLA) to participate in the PABC intervention, which uses established VA Health Care system technology and evidence-based intervention methods. The five key dimensions of feasibility to be assessed are whether Veterans: 1) can successfully participate in the intervention (practicality), 2) tolerate physical activity progression (implementation feasibility), 3) are interested and enjoy the intervention (acceptability), 4) complete the intervention safely (safety), and 5) respond to the intervention with increased activity and decreased disability (responsiveness).^{31,32} Measures of physical activity and disability will be used to establish effect size estimates for the PABC intervention, with the intention of planning a future clinical efficacy trial. Testing will occur at baseline (pre-intervention), three months (end of intervention), and six months, using a two-group randomized crossover design.

Primary Aim: Determine feasibility of using the PABC intervention with older Veterans who have dysvascular LLA by assessing: 1) practicality (measured by retention rate), 2) implementation feasibility (measured by dose goal attainment), 3) participant acceptability (measured by the Intrinsic Motivation Inventory (IMI) – Interest / Enjoyment Subscale), and 4) safety (measured with Adverse and Serious Adverse Events).

Hypothesis 1.1: Retention rate will be at least 85% over the PABC intervention period (i.e., ≤15% attrition).

Hypothesis 1.2: At least 75% of participants will meet the dose goal of a 3% average increase in daily steps per week, across the three months of intervention.

Hypothesis 1.3: Participants will indicate PABC intervention acceptability with a mean score of ≥ 5/7 on the IMI – Interest / Enjoyment Subscale.

Hypothesis 1.4: There will be similar rates of study related (definitely, probably, possibly) adverse events between groups during the first three months (period of direct comparison of intervention versus control).

Secondary Aim: Establish effect size estimates of the PABC intervention (responsiveness)

using physical activity and self-report disability outcomes.

Hypothesis 2.1: The PABC group will have increased activity counts and less self-reported disability than the control group at Month 3, each with effect size estimates ≥ 0.80 (Cohen's d).

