The FitBit sensor will be used to guide the intervention and data from the sensors will NOT include personal health information; with generic accounts will be created for each user without participant-identifiable information. FitBit data will not be used as outcomes, but rather, only to guide the PABC intervention. Outcome data will be managed using the REDCap (Research Electronic Data Capture) platform. REDCap is a secure, web-based application designed to support research data capture, providing user-friendly case report forms, real-time data entry validation (e.g., data type and range checks), audit trails, transaction logs, and a de-identified data export to common statistical packages. The VA Eastern Colorado Health Care System has approved REDCap for research use. More detail is provided in the Human Subjects section.

D.8. Sample Size Estimate

The sample size estimate was based on evidence for activity change in patients with DM and PAD, which indicates a reasonable expected increase of 3% walking activity per week (e.g., steps, distance, time) over 3 months.^{3, 12, 77, 78} A baseline mean (SD) of 2000 (900) steps/day was estimated based on data from our ongoing dysvascular LLA RCT (Section C.3.) and published LLA data.^{49, 79, 80} A 3% weekly increase in steps during intervention, assuming no order effect, would provide an effect size of 0.8 (Cohen's d). Based on those assumptions, a sample size of 13 per group with a crossover design (total n=26) provides >95% power to detect an intervention effect (effect size=0.8, $\alpha=0.05$, two-tailed paired t test). The study is generously powered intentionally, because the assumption of 'no order effect' will not likely hold. We will recruit 32 participants, and expect at least 26 to complete. This 15% attrition estimate is conservative, based on an historical attrition rate <15% in our intervention studies with other older adult populations^{81, 82} and our current dysvascular LLA RCT.

D.9. Data Analysis Plan

Aim 1 (Feasibility of PABC Intervention): The analyses for Aim 1 are based on four hypotheses: H1.1) participant retention, H1.2) dose goal attainment, H1.3) intervention acceptability, and H1.4) safety.

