- H1.1) Retention rate will be assessed using a cut off of 15% attrition (i.e., loss of >6 participants). Mean attrition rate will be compared to the null value of 15% using a one-sample t-test ($\alpha=0.05$). This attrition rate is considered feasible based on previous activity change programs for patients with DM or PAD.^{5, 83}
- H1.2) Dose goal attainment will be assessed by the proportion of participants achieving the goal of 3% average weekly increase in steps, based on activity gains in other intervention studies.^{3, 12, 78} The ability to attain a 3% average weekly step increase for <75% of the participants will be considered a negative result. The proportion of participants attaining a 3% average weekly step increase will be reported (95% CI) and compared to the null value of 75% using a one-sample binomial proportions test ($\alpha=0.05$).
- H1.3) Acceptability of the intervention will be measured with the IMI Interest and Enjoyment subscale, with a mean score of <5/7 considered a negative acceptability result.¹⁰ Mean IMI Interest and Enjoyment score will be compared to the null value of 5.0 using a one-sample t-test ($\alpha=0.05$).
- H1.4) Adverse and serious adverse event (AE/SAE) rates (events/participant) will be compared between groups for Months1-3 (PABC intervention for GROUP1, attention control for GROUP2). We expect similar AE/SAE rates between groups (assessed by Safety Officer and research team).

Aim 2 (Effect Size and Preliminary Efficacy of PABC Intervention): Effect size of the PABC intervention will be calculated with Cohen's d using mean and standard deviation for change in activity counts and LLFDI scores. Statistical inference of group differences for calculation of sample size estimates will be based on linear models with activity counts and LLFDI scores as outcome variables. Explanatory variables in each model will include primary medical diagnosis (PAD, DM, or both), group, and baseline activity count or LLFDI score.

D.10. Expected Outcomes and Interpretation

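### The Cohen's d that decides Hypothesis 2.1 is built from unadjusted change scores, so it moves with chance baseline imbalance that the linear model planned in the same paragraph would remove

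*Combined protocol and SAP*

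**What the plan says.** The Secondary Aim in section A is to estimate the effect size of the intervention. Hypothesis 2.1 sets the criterion: more activity and less disability in the PABC group "than the control group at Month 3, each with effect size estimates ≥ 0.80" on Cohen's d.

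Section D.9, Aim 2, gives two calculations. The effect size is "calculated with Cohen's d using mean and standard deviation for change in activity counts and LLFDI scores". Separately, "Statistical inference of group differences for calculation of sample size estimates will be based on linear models", and for these models "Explanatory variables in each model will include primary medical diagnosis (PAD, DM, or both), group, and baseline activity count or LLFDI score". Nothing in D.9 says that d is taken from the models.

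Section D stratifies randomization by amputation level only. Baseline activity and baseline LLFDI are therefore balanced by chance alone, with 16 randomized per group and about 13 per group expected to complete (D.8).

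**The concern.** A difference in mean change fixes the slope on baseline at 1. If rho is below 1, a group that happens to start low will tend to rise toward the common mean, and a raw change score counts that rise as effect. A group that happens to start high is penalized in the same way. Groups of 13 to 16 leave plenty of room for such imbalance.

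At stake is the one number that Hypothesis 2.1 is judged on. D.9 treats baseline as worth adjusting for in its inference but leaves it out of the quantity compared with 0.80. The d and the model can then point different ways purely because of the baseline draw, and the plan does not say which governs.

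**Working it through.** **Inputs.** "A baseline mean (SD) of 2000 (900) steps/day was estimated" (D.8). "A 3% weekly increase in steps during intervention, assuming no order effect, would provide an effect size of 0.8" (D.8). Completers: 13 per group, 26 in total (D.8). Rho is not in the documents, so it is an assumption, shown from 0.3 to 0.9.

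**1. The plan's own figures.** Twelve weeks at 3% of 2000, taken linearly, is 12 × 0.03 × 2000 = 720 steps/day, and 720/900 = 0.80. A two-sided paired t test at 0.05 with 26 pairs and d = 0.8 has 97.5% power, which agrees with the stated figure of more than 95%.

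**2. The rho that D.8 implies.** The SD of a difference is SD × √(2(1 − rho)). If 900 is both the baseline SD and the SD of differences, then 2(1 − rho) = 1 and rho = 0.5. This is an inference about steps per day, not a stated value.

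**3. Shift in the change-score d.** A baseline imbalance D moves the difference in mean change by −(1 − rho) × D. One standard error of imbalance is SD × √(2/n), which is 900 × √(2/13) = 353 steps/day. Dividing by the SD of change, the size of the shift in d is

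(1 − rho) × √(2/n) / √(2(1 − rho)) = √((1 − rho)/n).

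At rho 0.5 this is √(0.5/13) = 0.196 with 13 per group and √(0.5/16) = 0.177 with 16. The correlation between the change-score difference and the imbalance is −√((1 − rho)/2). The baseline-adjusted difference has correlation zero with it.

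**4. Precision.** The variance ratio, adjusted to change-score, is (1 + rho)/2 in large samples. It is then multiplied by 1/(1 − k/(N − 1)) for k estimated covariates. D.9's model has k = 3 (baseline plus two terms for three-level diagnosis). With N = 26 the multiplier is 1/(1 − 3/25) = 1.136. Diagnosis is assumed not to be prognostic.

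For 13 per group:

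| rho | Shift in d per 1-SE imbalance | Correlation with imbalance | SE ratio, full D.9 model (formula) | SE ratio (simulated) |
|---|---|---|---|---|
| 0.3 | 0.23 | −0.59 | 0.86 | 0.87 |
| 0.5 | 0.20 | −0.50 | 0.92 | 0.93 |
| 0.7 | 0.15 | −0.39 | 0.98 | 0.99 |
| 0.8 | 0.12 | −0.32 | 1.01 | 1.03 |
| 0.9 | 0.09 | −0.22 | 1.04 | 1.04 |

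The precision gain is gone once (1 + rho)/2 = 1 − 3/25 = 0.88, that is rho = 0.76 (about 0.81 with N = 32).

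**5. Effect on the 0.80 verdict.** In 8,000 simulated trials per setting, with 13 per group, rho 0.5 and a true effect of 0.8:

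- The change-score d reaches 0.80 in about 51% of trials overall. The figure is about 80% when PABC starts more than one standard error low and 20-23% when it starts more than one standard error high.
- The adjusted estimate gives about 50% in either case.
- Imbalance beyond one standard error, in one direction or the other, occurs in about one trial in three.

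With a true effect of 0.4, the chance of wrongly reaching 0.80, averaged over imbalance, falls from about 16% to 13% at 13 per group, and from about 13% to 10-11% at 16 per group.

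**The case against.** A fair opponent would say the following.

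- *The change score is unbiased under randomization.* This is true. The problem is conditional on the imbalance that this one trial draws. A reader might infer that the plan's d systematically overstates the effect; it does not.
- *No power is lost.* This also stands. D.9 plans no significance test on d; its inference on group differences already uses the adjusted models. A reader might infer that the trial loses power or that the whole of Aim 2 is compromised. The text confines the defect to the reported d and the Hypothesis 2.1 verdict.
- *The precision gain is small.* This stands. A baseline-only model would look better, but D.9 also includes diagnosis. With that model, power for a 0.8 SD difference at rho 0.5 goes from 50% to 56% at 13 per group and from 59% to 67% at 16, with almost no gain at rho 0.7 to 0.8. Sampling error in d, about 0.4 at 13 per group, stays large either way.
- *Rho = 0.5 is only inferred.* This stands. D.8 concerns steps in a paired crossover comparison. The documents give nothing for ActiGraph counts or LLFDI. Only the direction of the problem holds for every rho below 1.
- *D.9 names no time point.* Section D says the crossover supplies all 32 participants for both aims, which leaves room for a within-person d pooled over both groups' intervention periods. Hypothesis 2.1, however, is worded between groups at Month 3, and the point is made on that reading.
- *The standardizer matters more.* Divided by the SD of change, the same 720 steps gives d of 0.68, 0.80, 1.03, 1.26 or 1.79 at rho 0.3, 0.5, 0.7, 0.8 or 0.9. That spread is wider than the imbalance shift. It does not answer the concern, but any repair must name the denominator.

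**Conclusion.** The point holds in a limited form. Read as Hypothesis 2.1 words it, the plan judges the hypothesis on a d that carries chance baseline imbalance, while a model that removes it is already specified alongside. The main consequence is the conditional shift: about 0.20 in d for a one-standard-error imbalance with 13 per group at rho 0.5, and 0.12 to 0.23 over rho 0.8 to 0.3, against a cut-off of 0.80. The precision gain is secondary, at about 6-8% of the standard error at rho 0.5, about 0-2% at 0.7 and none at 0.8.

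These sizes rest on an assumed rho, equal SDs at the two times, a non-prognostic diagnosis term and 13 completers per group. The inference feeding the later trial's sample size is not affected, because it is already baseline-adjusted.

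**What to change.** In D.9 Aim 2 and Hypothesis 2.1, define d as the baseline-adjusted Month 3 difference between PABC and control, from the linear model already planned, divided by a named standardizer and reported with a 95% CI. The pooled baseline SD is a natural choice, because it is the scale on which D.8 obtained 0.80. Judge Hypothesis 2.1 on that value and report the change-score d as descriptive. Naming Month 3 and the between-group contrast in the same place also settles the time point that D.9 leaves open.

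The cost is a short edit to D.9 and a matching phrase in Hypothesis 2.1, with no new data, visits or participants. There is one small downside: the diagnosis term uses degrees of freedom and can cancel the precision gain when rho is high. The protection against baseline imbalance remains.

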The proposed pilot study is a randomized, tester-blinded design assessing PABC intervention feasibility (Aim 1) and effect size (Aim 2). Randomization ($n=32$) will create two groups (GROUP1 or GROUP2) using computer-generated random blocks of 2 and 4, stratified by amputation level (transtibial and transfemoral). An investigator not involved with testing or intervention ([name]) will conceal group allocation. A crossover design is used to simultaneously accomplish the aims and optimize recruitment (Fig.2). The PABC Intervention will be delivered to both groups (GROUP1 during Months 1-3 and GROUP2 during Months 4-6). The crossover design provides $n=32$ for assessing Aims 1 and 2. Intervention effect retention will be tested at six months for GROUP1 ($n=16$).

D.1. Setting

The study will occur at the VA Geriatric Research Education and Clinical Center (GRECC), where Drs. [name] and [name] have dedicated positions ([name] (GRECC Director)). Intervention delivery will occur with the participant at home and therapist at a VA site with access to tablet interface software (e.g. VA Jewell Motion Analysis Lab or VA Clinical Building South, using VA-supplied and approved mobile-health tablets and wearable activity sensors (FitBit)).

D.2. Participants

Thirty-two participants will be recruited from the Denver VAMC. The target sample is older Veterans diagnosed with PAD and/or DM, who have major LLA. We expect $<15\%$ attrition, with a goal of 26 participants completing.

D.3. Eligibility Criteria

Inclusion criteria: ≥ 50 years of age, LLA 1-5 years prior, Type II DM and/or PAD, and

ambulatory without human assistance, in the home or better using a prosthesis, with assistive device as needed, with assistive device as needed. Exclusion criteria: wheelchair as primary form of locomotion, trauma or cancer-related etiology of the LLA, unstable heart condition, uncontrolled hypertension, acute systemic infection, cancer, recent stroke (within 2 years), or lower extremity wound or ulcer that limits ambulation.

D.4. Recruitment Strategies

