- 1. Recruitment feasibility:** Recruiting 32 participants is challenging for a 2-year pilot study. The primary recruitment site will be the VAMC. Established relationships with 3 other regional hospitals will be used to expand recruitment, with a future protocol amendment as needed. In addition, recruiting Veterans with either transfemoral or transtibial LLA provides a larger recruitment pool than limiting the LLA to one specific level.
- 2. Functionality of the mobile-health technology:** Durability and continued functionality is a concern when using any technology. The mobile-health tablets used in this study are used in standard of care for a variety of purposes in the VA Eastern Colorado Health Care system. If a tablet becomes dysfunctional, replacement units are available for immediate replacement. The VA will provide mobile-health technical support for the duration of the study (See letter of support from [name]). Finally, the PABC intervention is not dependent on equipment brand, so future changes in equipment will not necessitate change in intervention.
- 3. Long-term behavior change:** Creating lasting change in physical activity behavior is a major challenge. We will collect data out to 6 months (GROUP1) to determine persistence of intervention effects. We expect activity changes may be reduced at the 6-Month time period compared to the 3-Month test point, but expect activity to remain higher than baseline, based on data from studies of patients with other chronic diseases.²
- 4. Transtibial and transfemoral LLA:** Response to intervention may differ between Veterans with transfemoral and transtibial LLA. We have included both levels of amputation, as both are linked to low activity and high disability. We will protect against such differences by stratifying randomization by level of amputation.

E. Study Timeline and Enrollment Goals:

TASK	Year 1				Total (1)	Year 2				Total (2)	TOTAL
Personnel Training											
Screening											
Enrollment (n=32)	4	4	6	6	20	6	6			12	32
Data Collection, Processing & Analysis											
Abstracts/Manuscripts											

F. Future Investigation:

This pilot project is an important stepping-stone for a larger research line focused on optimizing physical activity and minimizing disability for Veterans with dysvascular LLA. Data from this pilot study will inform a larger intervention trial targeting mobile-health physical activity change (future VA Merit Review proposal).

REFERENCES

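### The Aim 2 models omit amputation level, the randomisation stratum, so the standard error of the Month 3 group difference is too large if level matters beyond baseline

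*Combined protocol and SAP*

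**What the plan says.** Section D describes the allocation as made "using computer-generated random blocks of 2 and 4, stratified by amputation level (transtibial and transfemoral"). Section D.12, item 4, explains why: "Response to intervention may differ between Veterans with transfemoral and transtibial LLA", followed by "We will protect against such differences by stratifying randomization by level of amputation".

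Section D.9 (Aim 2) then states that "Statistical inference of group differences for calculation of sample size estimates will be based on linear models" and names the terms: "Explanatory variables in each model will include primary medical diagnosis (PAD, DM, or both), group, and baseline activity count or LLFDI score". Read with H2.1, the contrast is PABC against attention control at Month 3.

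No section puts amputation level into an Aim 2 model or any other analysis, and none gives a reason for leaving it out. The word for inclusion in D.9 could be read as a non-exhaustive list, but on that reading the plan still does not commit to the stratum.

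**The concern.** Stratifying makes the two groups alike in level, so the group difference varies less from one possible allocation to another. The ordinary least-squares standard error reflects that only if level is in the model. Without it, any part of the outcome that depends on level and is not carried by baseline is counted as noise, and the reported standard error is larger than the real variability of the estimate.

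At stake is the calibration of tests and intervals for the Month 3 difference, and some power, with about 26 people analysed. If the model's residual variance is carried into the sample size of the next trial, it would also be higher than with level included. D.12 relies on stratification alone to deal with level, while the model already spends two degrees of freedom on diagnosis, which is not a stratum.

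**Working it through.** **Inputs from the documents.** 32 randomised and at least 26 expected to complete (D.8), so 6 lost; blocks of 2 and 4 within level (D); model terms as in D.9; d = 0.8 and two-sided α = 0.05 (D.8; D.9 gives no α for Aim 2). For scale, D.8 says "A baseline mean (SD) of 2000 (900) steps/day was estimated".

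**Assumptions, not in the documents.** 35% transfemoral; baseline to Month 3 correlation ρ = 0.5; losses at random; level effect beyond baseline g from 0 to 1.0 outcome SD.

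**The plan's own figure.** 3% × 12 weeks × 2000 / 900 = 720 / 900 = 0.80. A two-sided paired t test with 26 pairs and d = 0.8 has 97.5% power (noncentral t), which agrees with the >95% in D.8. That is a within-person test and is not affected here. The Month 3 contrast is between groups: a two-sample t test with 13 per group and d = 0.8 has about 50% power, so the figures below lie in that region.

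**Residual variance, by formula.** With transfemoral share p, omitting level raises the residual variance by the fraction p(1 − p)g² / (1 − ρ²). Here p(1 − p) = 0.35 × 0.65 = 0.2275 and 1 − ρ² = 0.75. At g = 0.5: 0.2275 × 0.25 / 0.75 = 7.6%. At 0.8: 0.2275 × 0.64 / 0.75 = 19%. At 1.0: 0.2275 / 0.75 = 30%.

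**Simulation.** 20,000 trials per setting. Least squares with group, baseline and three-category diagnosis, without and with level:

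| g (SD) | Residual variance increase, level omitted | Mean model SE v true SD, omitted | Type I error, omitted | Power omitted | Power included |
|---|---|---|---|---|---|
| 0 | – | – | 4.9% | 55.5% | 54.6% |
| 0.2 | – | – | 4.8% | 54.8% | 54.6% |
| 0.3 | 3% | – | 4.7% | 54.0% | 54.6% |
| 0.5 | 8% | 0.375 v 0.370 | 4.4% | 52.0% | 54.6% |
| 0.8 | 20% | 0.396 v 0.378 | 3.7% | 47.7% | 54.6% |
| 1.0 | 32% | 0.414 v 0.385 | 3.2% | 44.0% | 54.6% |

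With level included, the mean model SE is 0.364 against a true SD of 0.369, and type I error is 4.9%. The mean estimate is 0.80 in both models. On the 900 steps/day scale, 0.3, 0.5 and 0.8 SD are 270, 450 and 720 steps/day.

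**Sensitivity** (10,000 trials each), power points lost at g = 0.3, 0.5 and 0.8:

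- 20% transfemoral: 0.0, 1.1, 4.4
- 50% transfemoral: 0.4, 2.6, 7.5
- ρ = 0.3: 0.1, 1.8, 5.6
- ρ = 0.7: 0.5, 3.7, 9.8

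**If level shifts baseline and Month 3 equally** by 0.5, 0.8 or 1.0 SD (ρ = 0.5), the loss is only 0.1, 0.9 or 1.7 points, because baseline absorbs most of it.

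**Is stratification the cause?** A second simulation used 12,000 trials per setting, residual SD set to 1, 25% or 40% transfemoral, and 6 of 32 lost. With level omitted, the ratio of model SE (root mean square) to true SD was about 1.00, 1.02, 1.05–1.06 and 1.10–1.12 at level effects of 0, 0.5, 1.0 and 1.5 residual SD. With level included it was 0.99–1.01. With unstratified allocation, 40% transfemoral and a level effect of 1.0, the model without level gave 0.469 v 0.469 and type I error 5.1%. The overstatement therefore comes from stratifying and then omitting the stratum.

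**The case against.** The strongest reply concerns size.

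- **Baseline may already carry level.** Participants are 1 to 5 years past amputation, and the models adjust for the baseline value of the same outcome. An effect of 0.8 SD beyond baseline is 720 steps/day, as large as the whole intervention effect assumed in D.8. Where level shifts baseline and Month 3 equally, simulations (6,000 trials per setting) at correlations of 0.7 and 0.8 show essentially no gain from adding level; for example, at a 0.8 SD shift, 71.1% v 71.3% and 85.0% v 84.9%. This stands: the larger losses need an effect that the documents do not support with data.
- **True precision hardly changes.** At 0.5 SD the true SD of the estimate is 0.370 without level and 0.369 with it; at 0.8 SD it is 0.378 and 0.369. This also stands. Stratification has already delivered most of the precision, and the fix mainly makes the reported standard error the right size.
- **The corrected model seems to understate slightly** (0.364 v 0.369). This does not stand. A mean of standard errors lies below the true value by a factor of about 1 − 1/(4 × 20) = 0.9875 on 20 degrees of freedom, and 0.369 × 0.9875 = 0.364. The t reference allows for this, and type I error is 4.9%.
- **D.12 speaks of differing response, not prognosis.** True. With a response 0.4 or 0.8 SD smaller in transfemoral participants, power omitted v included was 54.8% v 54.5% and 51.5% v 53.0%. A main effect does not estimate that difference.
- **No stated decision rests on this standard error.** H2.1 is judged on Cohen's d, which uses the SD of change, and H2.2 uses means and SDs. True, but D.9 does base inference on group differences on these models.

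**Conclusion.** The point holds. The randomisation is stratified by amputation level and the Aim 2 models leave level out. If level predicts Month 3 beyond baseline, the standard error of the group difference is overstated and inference is conservative, with no bias in the estimate.

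The size is modest and conditional. Under the stated assumptions, omission costs 0.6 points of power at 0.3 SD (54.6 − 54.0), 2.6 at 0.5 SD, 6.9 at 0.8 SD and 10.6 at 1.0 SD. It costs almost nothing if the effect is small or baseline absorbs it. The level effect, transfemoral share and baseline correlation are all assumed. Only the secondary aim is concerned, and any error is on the conservative side. The change is still worth making because it costs so little and the plan itself treats level as important enough to stratify on.

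**What to change.** In D.9, Aim 2, add *amputation level (transtibial/transfemoral), the randomisation stratum* to the explanatory variables of every activity-count and LLFDI model, as a fixed main effect. This aligns the analysis with the randomisation. It should not be described as testing whether response differs by level.

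The cost is one phrase and one degree of freedom: about one point of power (55.5% to 54.6%) if level turns out to be irrelevant. No new data are needed, since level must be recorded to randomise.
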